2.3 Study design and conduct

2.3.1 Study description

This is a Phase 3, multicenter, randomized, double-blind, placebo-controlled, noninferiority active reference study to evaluate the efficacy and safety of BKZ in subjects with active PsA who are biologic disease-modifying antirheumatic drug (bDMARD) naive. To be eligible to participate in this study, subjects must be adults with a diagnosis of active PsA based on the Classification Criteria for Psoriatic Arthritis (CASPAR) and have disease with TJC ≥ 3 and SJC ≥ 3 . In addition, subjects should not have been previously exposed to any bDMARD for PsA or PSO to be eligible for the study.

Approximately 840 subjects will be randomly assigned in a 3:2:1 ratio, stratified by region (North America, Western Europe, Eastern Europe, and Asia/Australia) and bone erosion (0, ≥ 1) to 1 of the 3 following blinded treatment groups:

- Bimekizumab 160mg sc Q4W (420 subjects),
- Placebo (280 subjects),
- Adalimumab sc 40mg every 2 weeks (Q2W) (140 subjects).

It is planned to enroll a minimum of 45% of subjects who have elevated hs-CRP (≥ 6 mg/L) and/or who have at least 1 bone erosion at Screening.

[figure not shown]
The overall study design consists of:

- a Screening Period (≥ 14 days to ≤ 35 days)
- a 16-week placebo controlled Double-Blind Treatment Period (DBP)
- a 36-week Active Treatment-Blind Period (ATP) (Week 16 to week 52)
- a Safety Follow Up (SFU) visit, 20 weeks after the final dose of IMP (for subjects not entering the open label extension (OLE) study or who discontinue early, including those withdrawn from IMP, as applicable).

The maximum study duration per subject will be up to 73 weeks.

The study schematic diagram for the study is presented in.

Figure 2-1: Study schematic diagram

ACR50=American College of Rheumatology 50% response criteria, BKZ=bimekizumab, PsA=psoriatic arthritis; Q2W=every 2 weeks, Q4W=every 4 weeks, sc=subcutaneous, SFU=Safety Follow-Up, W=week

^a Adalimumab dosing is performed every 2 weeks from Baseline to Week 50.

^b After 16 weeks of double-blind treatment, subjects will enter the Active Treatment-Blind Period. All subjects randomized to placebo will be reallocated to receive BKZ 160mg Q4W. Subjects randomized to BKZ 160mg Q4W will continue to receive their originally randomized dose. Subjects randomized to active reference (ADA) will continue with their active treatment.

^c Permitted rescue therapy is defined in Protocol Section 5.4.

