2.4.2 Power calculations for secondary endpoints

The assumptions for power calculations of the secondary endpoints included in the hierarchy, and for which supporting data exists, are based on the interim results of the Phase 2b BKZ study PA0008 and the FUTURE 1, FUTURE 2, FUTURE 5, and SPIRIT P1 studies. All power calculations for binary endpoints were performed using a 2-sided 2-sample Chi-square test with continuity correction (Fleiss et al, 1980). All power calculations for continuous endpoints were performed using a 2-sided 2-group Satterthwaite t-test (Moser et al, 1989).

For the PASI90 response at Week 16, the BKZ 160mg Q4W treatment response at Week 12 is 45% (n=20) in the TNF α -naïve population of PA0008 at Week 12 and 46% (n=28) at Week 12

in the mixed TNF α exposure population. The placebo PASI90 response at Week 16 is based on the subgroup analyses of TNF α therapy-naïve subjects in PA0008 (9.1% at Week 12; n=22), FUTURE 2 study (9.7% at Week 24; n=63), and SPIRIT P1 study (1.5% at Week 12; n=67). Therefore, a placebo PASI90 response rate of 10% is assumed. With those assumptions, the study has >99% power to detect a true treatment difference at an assumed 60% of subjects with BSA $\geq 3\%$ of the planned sample size.

For change from Baseline in HAQ-DI at Week 16, the between treatment differences of the change from Baseline in HAQ-DI of in the mixed TNF α exposure population of the PA0008 at Week 12 were used. The BKZ 160mg Q4W treatment group mean change from Baseline in HAQ-DI at Week 12 of -0.37, Standard deviation (SD)=0.47 (n=41) versus placebo mean change from Baseline in HAQ-DI at Week 12 of -0.13, SD=0.50 (n=42). With those assumptions, the study has >99% power to detect a true treatment difference of -0.24 at the planned sample size.

For change from Baseline in PCS of SF-36 at Week 16, the between treatment differences of the change from Baseline in PCS of SF-36 of the TNF α -naïve population of FUTURE 2 study (Kavanaugh et al, 2016) at Week 24 were used. The BKZ 160mg Q4W treatment group assumes the secukinumab 150mg treatment group mean change from Baseline in SF-36 PCS at Week 24 of 7.91, SD 7.38 (n=63) versus placebo mean change from Baseline in SF-36 PCS at Week 24 of 2.08, SD 9.51 (n=63). With those assumptions, the study has >99% power to detect a true treatment difference of 5.83 at the planned sample size.

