For dactylitis-free state at Week 16, dactylitis resolution data of the FUTURE 5 study (Mease et al, 2018) at Week 16 were used to estimate the BKZ 160mg Q4W treatment and placebo groups. The treatment effect estimate from the secukinumab 150mg treatment group at Week 16 of 56% (n=103) is assumed versus a placebo group estimate of 32% (n=124). With those assumptions and having 11% of subjects with Baseline dactylitis, the pooled PA0010/PA0011 studies have a 66% power to detect a true treatment difference of 24% (OR= 2.71).

For enthesis-free state at Week 16, enthesis resolution data from the FUTURE 5 study at Week 16 were used to estimate the BKZ 160mg Q4W treatment and placebo groups. In FUTURE 5 The treatment effect estimate from the secukinumab 150mg treatment group at Week 16 was 55% (n=141) and the placebo group estimate was 36% (n=192). Assuming a BKZ response of 55% and a placebo rate of 39% and having 25% of subjects with Baseline enthesis the pooled PA0010/PA0011 the studies have a 69% power to detect a true treatment difference of 16% (odds ratio 1.91). Treatment difference in change from Baseline in vdHmTSS at Week 16 in the overall population is estimated using the data from the FUTURE 5 study in a mixed TNF α exposure population. The BKZ 160mg Q4W group treatment difference compared to placebo is estimated to be the same as the difference in change from Baseline in vdHmTSS at Week 16 between the secukinumab 150mg group and placebo which is 0.42, assuming a SD of 1.13 for BKZ and SD=2.44 for placebo. With these assumptions the study has 76% power to detect a treatment difference of 0.42 in the planned sample size.

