- Step 4 (for primary and secondary efficacy variables): For each value of the imputation number from 1 to 100, the change from Baseline will be analyzed using and ANCOVA model with treatment group, region and bone erosion as fixed effects and the Baseline value as covariate. The results obtained from the 100 ANCOVA analyses (ie: the LSM for the treatment difference and the 95% CI for the contrasts) will be combined using Rubin's rules (via SAS® PROC MIANALYZE).

For composite continuous endpoints, the MI will be applied on each component the same way as for composite binary endpoint. The datasets obtained for each component will be merged by imputation number and subject number. On the dataset obtained, the endpoint will be derived for each subject/visit based on the component values. The endpoint obtained will be analyzed as above.

Ordinal efficacy endpoints

For ordinal efficacy endpoints, the MI method will be applied as for the continuous efficacy endpoints with the following exceptions:

- After the imputation of the intermittent and monotone missing data, the rounding rules will be performed to align the data with the possible responses for the respective endpoint (eg: If the variable can take the value 1, 2 or 3, the imputed values will be rounded to the closest possible value).
- If the ordinal efficacy endpoint is used to derive a binary endpoint, the same analysis strategy as described above for the binary endpoints will be used.
- If the ordinal efficacy endpoint is not used to derive a binary endpoint, the unadjusted proportions of subject by categories will be presented.
- If subjects have an IE, then the ordinal endpoint at all subsequent visits (from the day after the IE date, whether the data were observed or not) will be set to the value used for the worst category.

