- c. *Imputation.* Impute missing values for visit t using previous outcomes for visits 1 to t-1, bone erosion at Baseline, and region. Note that only placebo data will be used to estimate the imputation model since no outcome is available for BKZ-treated subjects at visit t. As a consequence, the input dataset should include all subjects from Placebo but only subjects from the BKZ arm that have values at timepoint t missing.
- d. Repeat steps 2a-2d for all timepoints after Baseline up to Week16, 100 times with different seed values (seeds ranging from 201 to 300) to create 100 imputed complete datasets. Subjects whose missing values were imputed in the last SAS® PROC MI call will be included in the input dataset for the next SAS® PROC MI call. Standard rounding rules will be applied to the imputed values. If the MI procedure yields a value outside of the pre-defined range for the given variable, the value will be updated to be within the predefined range of values for the endpoint of interest. For example, the imputed value for TJC will be updated to 0 or 68 in the case of an imputed value less than 0 or greater than 68, respectively.

2. The analysis will be done on the change from Baseline, and the model will be an ANCOVA model with treatment group, region, and bone erosion classification as fixed effects and the Baseline value as covariate.

For generation of summary statistics, the 100 imputed datasets will be combined, and simple means and standard errors will be calculated using Rubin's rules (via SAS® PROC MIANALYZE). For calculation of other descriptive statistics (median, Q1, Q3, minimum and maximum), Rubin's rules do not apply. MI estimates will be computed by calculating arithmetic means of the estimates from the multiple repetitions of the imputation algorithm. Thus, for median, Q1, Q3, minimum and maximum the following approach will apply:

- The data will be summarized by treatment, visit and imputation and the summary statistics will be computed.
- Results will be summarized by taking the mean value of each summary statistic at each visit across all imputations.
- The number of decimal places will remain the same as the original for display purposes (ie, if the mean was presented to 1 decimal place, the mean of the means will also be presented to 1 decimal place).

3. The results obtained from the 100 ANCOVA analyses in Step 4 (i.e. LSM for the treatment difference and the 95% CI for the contrasts) will be combined with Rubin's rules.

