4.5 Multiple comparisons/multiplicity

A step-down closed testing procedure will be applied for the primary endpoint and some secondary endpoints. The testing procedure will account for multiplicity and control the family-wise type I error rate at alpha=0.05 (2-sided).

For each test, on each binary efficacy endpoint, the null hypothesis is that the conditional odds ratio is equal to one ($H_0: OR_{T1T2} = 1$). The alternative hypothesis is that the conditional odds ratio is not equal to one ($H_A: OR_{T1T2} \neq 1$).

For each test, on each continuous efficacy endpoint, the null hypothesis is that there is no difference between treatment groups ($H_0: T_1 - T_2 = 0$). The alternative hypothesis is that there is a difference between treatment groups ($H_A: T_1 - T_2 \neq 0$).

T_1 refers to BKZ and T_2 to placebo.

According to this strategy, the statistical testing of an endpoint can be investigated only if the null hypothesis for the previous endpoint has been rejected (i.e., if $p < 0.05$). [Table 4-5](#) shows the testing order for these endpoints.

Table 4-5: Sequential testing procedure of primary/secondary efficacy endpoints (fixed sequence testing procedure) (All efficacy endpoints at Week 16)

BKZ 160mg Q4W	
H_1	ACR50 Response superior to Placebo
H_2	Change from Baseline HAQ-DI superior to Placebo

BKZ 160mg Q4W	
H ₃	PASI90 Response superior to Placebo
H ₄	Change from Baseline SF-36 PCS superior to Placebo
H ₅	MDA superior to Placebo
H ₆	Change from Baseline vdHmTSS* superior to Placebo on subjects with elevated hs-CRP and/or with at least one bone erosion (hs-CRP ≥ 6 mg/L and/or erosion-positive)
H ₇	Enthesitis-free state superior to Placebo (based on pooled PA0010 and PA0011 W16 data)
H ₈	Dactylitis-free state superior to Placebo (based on pooled PA0010 and PA0011 W16 data)
H ₉	Change from Baseline vdHmTSS** superior to Placebo

ACR=American College of Rheumatology; BKZ=bimekizumab; CfB=change from Baseline; H=hypothesis;

HAQ-DI=Health Assessment Questionnaire - Disability Index; hs-CRP=high sensitivity C-reactive protein;

LEI=Leeds Enthesitis Index; MDA=Minimal Disease Activity; PASI=Psoriasis Area and Severity Index.

PCS=Physical Component Summary; Q4W=every 4 weeks; SF-36=Short-Form 36-item Health Survey;

vdHmTSS=Van der Heijde modified Total Sharp Score.

* It is planned to enroll a minimum of 45% of subjects who are positive for elevated hs-CRP (hs-CRP ≥ 6 mg/L) and/or who have at least 1 bone erosion at Screening.

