- If the total score is missing at a post-Baseline visit (ie, only "N" or "S" is recorded for all joints) or if JSON or ES score is missing then the missing total score will be imputed using MI imputation.

For the change from Baseline analyses, subjects who withdraw early and have radiographs taken at their early withdrawal visit should be included in the analysis. In such cases, one or more imputation methods may be applied for the subjects with less than 2 radiographs. In addition to any such imputation approach that is selected, an analysis excluding subjects with less than 2 radiographs from the analysis should be performed.

In the testing hierarchy (Table 4-5), 2 endpoints are defined based on the vdHmTSS:

- Change at Week 16 from Baseline in vdHmTSS for subjects with elevated hs-CRP and/or with at least one bone erosion at Baseline (planned to be approximately 45% of the overall population). This is the 6th endpoint in the sequential testing hierarchy.
- Change at Week 16 from Baseline in vdHmTSS for all subjects. This is the 9th endpoint in the sequential testing hierarchy.

The 2 endpoints will be analyzed in the radiographic set.

At Week 16, imaging data collected outside ± 14 days of the expected visit date will be excluded from the analysis.

For the Week 24 interim analysis only, in the primary analysis of these 2 endpoints, missing data at Week 16 will be imputed based on value at Screening (as there is no value collected in between) using MI-MCMC / Monotone regression. Since VdHmTSS is only collected at Baseline prior to Week 16, only the second MI step to address monotone missing pattern and generating 100 imputations will be processed (Section 4.2.2.2).

8.2.1.6 Enthesitis-free state at Week 16 in the subgroup of subjects with enthesitis at Baseline

The Leeds Enthesitis Index (LEI) consists of 6 items, 3 for the right part and 3 for the left part of the body. The body parts are Lateral epicondyles of the humerus, Medial femoral condyle, and

Achilles tendons. Each item is scored for tenderness with either 1 or 0 (tenderness, no tenderness, respectively). The total score ranges from 0 (no enthesitis) to 6 (severe enthesitis).

Note that LEI is collected for all subjects regardless of their Baseline score.

In case 4 items are missing, the LEI will be set to missing. If at least 3 items are available, the available items will be assessed and scored and then weighted by the number of the assessed items (AI) as shown in the formula below:

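### H9 (vdHmTSS, overall population) is planned with very unequal SDs and an unequal-variance test, but the ANCOVA that tests it has no arm-specific or robust variance; at the planning SDs its nominal 95% CI covers about 91.5%.

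*SAP*

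**What the plan says.** **Planning.** SAP Section 2.4.2 states that "All power calculations for continuous endpoints were performed using a 2-sided 2-group Satterthwaite t-test". For H9 it takes a treatment difference of 0.42, "assuming a SD of 1.13 for BKZ and SD=2.44 for placebo", and reports 76% power at the planned sample size. Section 2.3.1 plans 420 subjects on BKZ and 280 on placebo.

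**Analysis.** For continuous endpoints in the hierarchy, Section 4.2.2.3 (reference-based imputation) says "the model will be an ANCOVA model with treatment group, region, and bone erosion classification as fixed effects and the Baseline value as covariate". Step 4 of Section 4.2.2.2 (monotone regression) calls for an "ANCOVA model with treatment group, region and bone erosion as fixed effects and the Baseline value as covariate". For the Week 24 analysis, Section 8.2.1.5 sends vdHmTSS to the monotone-regression method, so Section 4.2.2.2 governs H9 there. Section 8.2.2 carries over the model of Section 8.1.4.4, which is run in PROC MIXED. None of these sections mentions a residual variance by treatment group, a robust standard error or a Satterthwaite adjustment.

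**Hypothesis.** Under Section 4.5, for each continuous endpoint "the null hypothesis is that there is no difference between treatment groups", written as a difference of zero. Section 8.2.1.5 says of the overall-population vdHmTSS analysis: "This is the 9th endpoint in the sequential testing hierarchy".

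**The concern.** The SAP sizes H9 with a test that allows the two variances to differ. It then analyses H9 with a model that, as written, forces them to be equal. The words common variance do not appear; this is inferred from an ANCOVA with no variance option stated, which has one residual variance by default.

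The direction matters. When the larger arm has the smaller variance, the pooled residual variance is weighted towards the quieter arm and understates the error of the treatment contrast. A larger sample does not cure this, because the ratio of the two standard errors depends on the allocation and the SDs and not on the total number. At stake are the coverage of the reported 95% CI for the mean difference and the p-value of a confirmatory test.

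**Working it through.** **Inputs.** n = 420 (BKZ) and 280 (placebo), from Section 2.3.1. SDs 1.13 and 2.44, difference 0.42 and stated power 76%, from Section 2.4.2. Two-sided 0.05, from Section 4.5. All figures below are for complete data with normal errors.

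**1. Reproduce the stated power (unequal variances).**
- SE = √(1.13²/420 + 2.44²/280) = √(0.00304 + 0.02126) = 0.1559, with about 360 Satterthwaite degrees of freedom.
- 0.42/0.1559 = 2.69. Power is 76.6% by the noncentral t and 76.9% by the normal approximation. The stated 76% is reproduced.
- A pooled-variance power formula would give Φ(0.42/0.1368 − 1.96) = 86.6%, so the stated figure does rest on unequal variances.

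**2. Standard error under one residual variance.**
- Pooled SD = √[(419 × 1.13² + 279 × 2.44²)/698] = 1.774.
- Pooled SE = 1.774 × √(1/420 + 1/280) = 1.774 × 0.07715 = 0.1368.
- Ratio to the true SE = 0.1368/0.1559 = 0.878, about 12% too small.

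**3. Consequence.**
- Effective critical value = 1.963 × 0.878 = 1.72.
- Size for equal means = 2 × [1 − Φ(1.72)] = 8.5%. CI coverage = 100 − 8.5 = 91.5%.
- 20,000 simulated trials of the ANCOVA with treatment, region, erosion and Baseline gave 8.5% as well. With a heteroscedasticity-consistent (HC3) standard error, the simulated size was 4.9% and power 75.6%.

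**4. Sensitivity of the H9-level size (BKZ SD fixed at 1.13).**

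| Placebo SD | Size |
|---|---|
| 2.44 | 8.5% |
| 2.0 | 7.7% |
| 1.5 | 6.3% |
| 1.13 (equal) | 5.0% |

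If 5% to 15% of BKZ values were imputed with placebo-like spread (an assumed range), 8.5% becomes 8.2% to 7.6%. Section 4.2.2.2, unlike Section 4.2.2.3, does not limit the model to two arms. If 140 adalimumab subjects share the residual variance, the size is 10.2% at an adalimumab SD of 1.13 and 6.5% at 2.44; both SDs are assumptions.

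**5. Other continuous endpoints in the hierarchy.**
- H4 (SF-36 PCS, SDs 7.38 and 9.51): pooled SE 0.640 against true SE 0.673, ratio 0.951, size about 6.2%. Planned power exceeds 99%.
- H6 (vdHmTSS in the elevated hs-CRP and/or erosion subgroup): 4.8% at SDs 0.72/0.71. At 0.81/0.93 it is 5.5% with 45% of each arm and 5.6% at the full arm sizes.

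**The case against.** **The 8.5% is conditional.** It needs equal means together with the planned difference in SDs. If the drug did nothing, the SDs would be equal and the size 5%. This stands. It does not rescue the confidence interval, which has to cover when the drug works, and that is the planning scenario.

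**Family-wise error.** A reader might infer that the trial's 5% family-wise control fails. The documents do not support that. H9 is last and is reached only after H1 to H8 are all rejected. Taking H1 to H5 as certain and treating the SAP's powers for H6, H7 and H8 (95%, 69%, 66%) as independent, a false H9 rejection would occur in about 0.95 × 0.69 × 0.66 × 8.5% = 3.7% of trials. H6 is also a subset of the H9 population. With an effect of −0.30 in 45% of subjects, a zero overall effect would need about +0.25 in the rest (0.45 × 0.30/0.55).

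**The SD pair is borrowed and may not apply.** It comes from a trial with mixed TNFα exposure, whereas this trial enrols bDMARD-naive subjects. The SAP's subgroup SDs are far smaller and nearly equal. If 45% of placebo subjects had SD 0.71, an overall 2.44 would need about √[(2.44² − 0.45 × 0.71²)/0.55] = 3.2 in the others, ignoring any difference in subgroup means. This is fair, and it is why a range is given. The pair is nevertheless what the SAP assumes for H9.

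**Planning and analysis need not use the same test.** True, and the unequal-variance calculation gave the more cautious power. Using different methods is no error in itself. The difficulty is that the analysis method is anti-conservative under the planning assumptions.

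**Imputation and analysis set.** The figures ignore Rubin's rules, which may offset a little of the excess, and the Radiographic Set may hold fewer than 420 and 280 subjects. Both qualifications stand; neither removes the effect.

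**Conclusion.** The point holds for H9 in a conditional form. At the SAP's own SDs and allocation, an ANCOVA with one residual variance understates the standard error by about 12%, the nominal 95% CI covers about 91.5%, and the H9-level test of equal means has size about 8.5%. The excess shrinks as the SDs converge and vanishes when they are equal. The conclusion rests on reading an ANCOVA without a variance option as having a single residual variance, on the planned arm sizes, and on complete data.

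No family-wise inflation is established. H4 is mildly affected, at a planned power that makes a changed decision unlikely, and H6 essentially is not. The change is worth making because it protects the interval estimate and the H9 p-value, and aligns the analysis with the test behind the stated 76%.

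**What to change.** In Sections 4.2.2.2 (Step 4) and 4.2.2.3, add a sentence for vdHmTSS in the overall population (H9). In each imputed data set, before Rubin's rules, the ANCOVA is fitted in PROC MIXED with treatment-specific residual variances (REPEATED with GROUP=treatment) and Satterthwaite or Kenward-Roger degrees of freedom, or a heteroscedasticity-consistent standard error is used. Both sections need the sentence, because Section 8.2.1.5 makes the imputation method differ between the Week 24 analysis and later ones. The same wording could optionally cover the other continuous hierarchy endpoints for consistency; H6 does not require it.

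The cost is one sentence and about one line of code in a procedure already planned. The downside is a less favourable H9 p-value if placebo proves the more variable arm. At the planning SDs, power falls from about 83% for the single-variance test to about 76%, the figure the SAP already states.
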